SAFETY OF ISOSORBIDE MONONITRATE: The FDA indication for IMN is for prevention of angina pectoris (<https://druginserts.com/lib/rx/meds/imdur/>). Per the package insert as referenced in link, there is no evidence of carcinogenicity, gene mutation or chromosome aberrations at biologically relevant concentrations. Side effects include nausea, dizziness, headache, symptomatic hypotension

1
2
3
4
5
6
7
8
9
10
11
12
13
14
15
16
17
18
19
20
21
22
23
24
25
26
27
28
29
30
31
32
33
34
35
36
37
38
39
40
41
42
43
44
45
46

MATERIAL AND METHODS:

Study Population: Adult patients who are referred to the Adult Nephrology Clinic at The University of Texas Health Science Center at Houston for evaluation and treatment of acute kidney injury, hypertension and/or proteinuria while either on or enrolled with anti-VEGF therapies, will be included in the study. The protocol is currently being submitted to the University of Texas Health Science Center at Houston IRB. Informed consent in the native language of each patient will be obtained prior to enrollment.

Inclusion Criteria: Patients on or enrolled for anti-VEGF therapy and having new-onset proteinuria, defined as a urine protein: creatinine ratio (UPC) of >500mg/g or hypertension (Systolic BP \geq 140 mm Hg and/or diastolic BP \geq 90 mm Hg) or a decrease in eGFR by \geq 25% from baseline before starting therapy.

Exclusion Criteria: Pregnant women and breast-feeding women. Patients >65 years will be excluded.

Protocol and Treatment Plan: The patients will have baseline blood pressure (BP), UPC, weight, serum basic metabolic panel and eGFR measured prior to being assigned into groups. All current prescribed and over the counter medications will be documented. Patients will be allocated to the treatment or placebo arms by simple randomization. BP will be measured in the right arm of patients, in the seated position, using arm cuff and automated office blood pressure by oscillometry method. Three measurements will be taken one minute apart, and the average of each of the systolic and diastolic measurements will be charted as the blood pressure recording for the visit. Pregnancy and breast feeding status will be established by self-reporting by female patients.

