7 appointments would be +/- 3 days to account for clinic closure, weather changes or patient's inability to
8 come to clinic due to non-medical reasons. A follow up phone call will be done every month (weeks 6,
9 10, 14 and 17 weeks) for 3 months. Antihypertensive medications that the patients have been taking
10 prior to enrollment will be continued. Any reduction in the need for antihypertensive medications will
11 be documented. UPC will be measured at the time of enrollment and then monthly.

12
13 **Primary End Points:**

- 14
- Reduction in UPC of $\geq 25\%$ from that measured before enrollment

15 **Secondary End Points:**

- 16
- Improved eGFR $\geq 25\%$ from before enrollment.
 - Reduction in SBP of ≥ 10 mm Hg and/or DBP ≥ 5 mm Hg from before enrollment
- 17
18

19 Both the primary and secondary outcomes will be measured for every month for the 3 months that the
20 patient is in the trial. All patients will continue treatment for the entire 3 months to help with data analysis
21 for future larger randomized controlled studies. The grace period for follow up appointments would be
22 +/- 3days to account for clinic closure, weather changes or patient's inability to come to clinic due to
23 non-medical reasons.

24 **MONITORING/ EVALUATION DURING STUDY:**

25 Baseline BP, serum creatinine, eGFR, and UPC will be recorded at the time of enrollment. For blood
26 testing 2cc of serum will be collected and for urine testing 2 ml of urine will be
27 collected, and sent to the Memorial Herman outpatient laboratory. Blood pressure will
28 be monitored on a weekly basis starting from the time of enrollment. In those who are already on BP
29 medications, BPs will be recorded on a weekly basis, and any need for reduction/increase in the
30 doses/addition of new medications will be document. Patients will be given a log book
31 to record their BPs. Patients will be monitored for 3 months. UPC and serum creatinine will
32 be measured on a monthly basis.

33 If side effects (nausea, dizziness, headache, symptomatic hypotension) are observed to the increased
34 dose of 120 mg/day, the dose will be reduced back to the 60 mg d.

35 **Confidentiality Plan:**

36 All data obtained, including concomitant medications will be entered in Red Cap. All serious adverse
37 events will be forwarded to FDA according to the UT Health Science Center at Houston institutional
38 policy. All records will be maintained at UT Heath Science center. The Data Safety Monitoring board

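### Pregnant women are excluded, but status is established by self-report alone, so an unrecognised pregnancy would not be detected before randomisation

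*Protocol*

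**What the plan says.** The exclusion criteria under Material and Methods are short: "Exclusion Criteria: Pregnant women and breast-feeding women. Patients >65 years will be excluded". The Study Population paragraph opens entry to "Adult patients who are referred to the Adult Nephrology Clinic" and sets no limit by sex or childbearing potential.

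The Protocol and Treatment Plan paragraph lists what is done before allocation: "The patients will have baseline blood pressure (BP), UPC, weight, serum basic metabolic panel and eGFR measured prior to being assigned into groups". It ends by stating how the pregnancy criterion is applied: "Pregnancy and breast feeding status will be established by self-reporting by female patients".

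Urine is already part of enrollment. The Follow-up section says "UPC will be measured at the time of enrollment and then monthly", and Monitoring/Evaluation During Study repeats the baseline measurements and gives the sample volumes: "testing 2cc of serum will be collected and for urine testing 2 ml of urine will be" collected and sent to an outpatient laboratory.

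**The concern.** An exclusion criterion works only as well as the method used to apply it. Here the criterion covers all pregnant women, while the method can identify only those who already know that they are pregnant. A woman early in an unrecognised pregnancy would truthfully report that she is not pregnant, pass screening and be randomised.

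At stake is whether the trial can keep its own eligibility rule. A patient whom the protocol means to keep out could be assigned to three months of study treatment, and nothing in the baseline work-up would show the error. How eligibility is established belongs in the protocol, and this protocol settles it explicitly. The point therefore concerns a stated method, not a detail that a statistical analysis plan might supply.

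**Working it through.** No formula applies, and the protocol gives no figure on this point to reproduce. The check sets the relevant statements side by side.

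1. **Who is excluded.** Exclusion Criteria: "Pregnant women and breast-feeding women", without qualification. The criterion refers to pregnancy itself, not to known pregnancy.

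2. **Who can enter.** Adults, with an upper age limit of 65 and no restriction by sex. The protocol contains no definition of childbearing potential and no contraception requirement. Women who could be pregnant are therefore within the eligible population.

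3. **How status is established.** By self-report only (Protocol and Treatment Plan). The protocol names no urine or serum pregnancy test at any time point.

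4. **Whether another baseline item would fill the gap.** The list before allocation is blood pressure, UPC, weight, basic metabolic panel and eGFR. The list under Monitoring/Evaluation During Study is blood pressure, serum creatinine, eGFR and UPC. No item on either list is a test for pregnancy.

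5. **What follows.** From items 3 and 4, a pregnancy unknown to the woman cannot be picked up before randomisation by any step the protocol states.

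6. **Whether a test would fit.** UPC is measured before assignment, so urine is obtained at the right moment. The stated volume is 2 ml. Whether that also suffices for a second test is not addressed.

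7. **Size.** Study design plans 20 patients per group, 2 × 20 = 40 in all. The protocol gives no proportion of women, no age distribution and no pregnancy rate, so the expected number of missed pregnancies cannot be calculated. One wrongly included patient would be 1/20 = 5% of a planned arm, so could move that arm's responder proportion by at most 5 percentage points. Randomisation means that such a patient is as likely to fall in either arm, so there is no systematic direction to the error.

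**The case against.** The strongest reply is that the protocol is consistent: it states an exclusion and a way of applying it, and neither sentence contradicts the other. The harm is not shown in the document, no rate is given, and the oncology service may already test for pregnancy before anti-VEGF therapy. The consent material is not in the file, so what participants are told about pregnancy or contraception cannot be judged.

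Much of this stands. It limits the point to a weak method rather than an inconsistency, and it lowers the priority. It does not remove the gap. The protocol neither requires nor relies on a test done elsewhere, and it admits patients who are only enrolled for anti-VEGF therapy, so earlier testing cannot be taken for granted.

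A reader might also infer three stronger points, which the document does not support.

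- **Fetal exposure to an ACE inhibitor as a harm of the trial.** Study design makes an ACE inhibitor one of two background options, given as needed for hypertension as standard of care. It is not a treatment that the trial adds for everyone. The exposure the trial itself adds is isosorbide mononitrate, for which the protocol states no fetal hazard. Its Preliminary Studies section describes organic nitrates being studied as a treatment in preeclampsia.
- **Pregnancy counted as anti-VEGF kidney injury.** Preliminary Studies likens the renal changes of anti-VEGF therapy to those of preeclampsia. That does not show that a pregnancy still unknown to the woman produces the entry findings, and only unknown pregnancies escape self-report.
- **A need for monthly retesting.** Urine is taken monthly, but a repeat test would need a rule for what happens to study treatment after a positive result. That is a clinical decision for the sponsor and goes beyond the point made here, which is detection before randomisation.

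**Conclusion.** The point holds as a low-priority safety improvement. The protocol excludes pregnant women and then fixes a method that cannot detect an unrecognised pregnancy, although urine is already collected before assignment.

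Its size cannot be put in figures from the document. Two judgements support the low priority: that unrecognised pregnancy is rare among 40 oncology patients, and that the effect on the comparison of arms is therefore probably negligible. Neither rests on a rate in the protocol. The case for change is that the exclusion should do what it says and that the remedy costs little. It does not depend on a threat to the trial's conclusions.

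**What to change.** In the Protocol and Treatment Plan paragraph, limit self-report to breast-feeding and state a test for pregnancy. For example: women of childbearing potential, as defined in this protocol, must have a negative urine pregnancy test at the enrollment urine collection before randomisation. The sponsor should supply the definition of childbearing potential.

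The cost is one inexpensive test for a subset of at most 40 patients, a short amendment and no additional visit. The volume under Monitoring/Evaluation During Study ("for urine testing 2 ml of urine will be" collected) may have to be raised above 2 ml. The result must be available before allocation, as the baseline UPC already must be.

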PRELIMINARY STUDIES: Cancer patients receiving anti-VEGF therapy share similar pathophysiological renal changes as seen in women with preeclampsia^{8,9}. Endothelial dysfunction in preeclampsia results from reduction in NO bioavailability⁴. Interestingly, eNOS uses nitrates as a substrate, and hence several studies have examined the utility of using organic nitrates as a possible treatment for NO deficiencies in preeclampsia. Although these studies were not powered to identify alterations in maternal and fetal outcomes, they did highlight the potential use of organic nitrates as antihypertensive agents in pre-eclampsia^{5,6,7}. Moreover, recent studies have shown that NO donors normalize blood pressure in anti-VEGF induced hypertension¹⁰. The same authors went on to devise a treatment algorithm distinguishing three groups of patients on anti-VEGF treatment: normotensive (<120/<80 mm Hg); prehypertensive (120-130/80-89 mm Hg) and hypertensive (>140/>90 mm Hg). They suggested no pharmacological treatment for normotensive patients, starting NO donors only for those pre-hypertensives with evidence of organ damage, and starting with NO donors as antihypertensive agents for the hypertensives along with weekly blood pressure checks¹¹. In their paper, they suggest that pre-treatment with long lasting NO donors may protect against the development of VEGF pathway inhibitor (VPI)- induced hypertension. They suggest the start of treatment 7-10 days before the initiation of VPI therapy. The paucity of large clinical studies in the literature using NO donors to protect against the development of proteinuria and hypertension and cancer patients receiving VPI therapy prompted us to investigate this modality of treatment.

RATIONALE OF DOSE: Preliminary data from a trial done to study single dose effects of isosorbide mononitrate (IMN) alone or in combination with losartan on central blood pressure showed that the mean placebo-subtracted decrease from baseline in augmentation index was highest in those patients who received 60 mg IMN with or without losartan¹². An effectiveness of extended release nitrate study for treatment of systolic hypertension used 60 mg and 120 mg strength tablets and showed statistically significant changes in the augmentation index and decreasing pulse pressure¹³. No studies have checked the effect on proteinuria. Accordingly, 60 mg and 120 mg of IMN will be used in the present study

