Patients in the treatment arm will be started on IMN 60 mg ER daily. The dose of IMN will be escalated to 120 mg ER (two tablets of 60 mg ER) after 4 weeks of start of therapy, if no response as per our response criteria (as below) is achieved. The grace period for follow up appointments would be +/- 3days to account for clinic closure, weather changes or patient's inability to come to clinic due to non-medical reasons.

The drug and placebo will be compounded in Compounding Shop Pharmacy, [name]. Even though we will be using the drug for a non-FDA approved use of IMN, we will not be needing IND for the study drug due to the low risk profile of the drug. Drug accountability by IDS will include for storage, labeling, dispensing and disposal of the study drug and placebo.

Criteria for Response (one or more of the following)

1. Improved eGFR \geq 25% from prior to enrollment.
2. Reduction in proteinuria of \geq 25% from prior to enrollment.
3. Reduction in SBP of \geq 10 mm Hg and/or DBP \geq 5 mm Hg from prior to enrollment

Study design:

The patients will be allocated by simple randomized into the two groups (20 patients per group). The study will be double-blinded

Group 1: (Treatment group). The starting dose will be Imdur 60 mg ER daily and after 4 weeks, if tolerated but response is not achieved, the dose will be escalated to Imdur 120 mg ER daily (2 tabs of 60 mg ER tablets). This would be done in addition to the standard of care treatment with either angiotensin converting enzyme inhibitor (ACEI) or calcium channel blockers to treat hypertension as needed.

Group 2: (Placebo group): Placebo will be given along with the standard of care treatment with either ACE I or calcium channel blockers to treat hypertension as needed. The tablets of placebo will be doubled after 4 weeks of start of therapy. This will help eliminate bias in this double-blinded study.

1
2 **Follow-up:** Systolic BP will be monitored on a weekly basis for three months. The patients will
3 record their BPs at home with their automated machines and will either call in with the results or bring
4 their records during the next clinic visit. The eGFR and serum creatinine (included in the basic
5 metabolic panel) will be measured as per protocol laboratory workup done within 15 days of
6 enrollment. This will be done once a month during clinic visits. The grace period for follow up

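### Simple randomisation does not deliver 20 patients per group and ignores baseline UPC; concealed blocks stratified on UPC would be a cheap, optional improvement

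*Protocol*

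**What the plan says.** The allocation method is fixed twice. Under Protocol and Treatment Plan: "Patients will be allocated to the treatment or placebo arms by simple randomization". Under Study design: "The patients will be allocated by simple randomized into the two groups (20 patients per group". The protocol names no block, stratum, minimisation factor or cap on either arm. The 1:1 ratio is implied by the equal group sizes.

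The other passages that bear on this are:

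- Protocol and Treatment Plan, on timing: "The patients will have baseline blood pressure (BP), UPC, weight, serum basic metabolic panel and eGFR measured prior to being assigned into groups".
- Inclusion Criteria: entry is by any one of three routes, "having new-onset proteinuria, defined as a urine protein: creatinine ratio (UPC) of >500mg/g or hypertension" or a fall in eGFR of at least 25%. A patient can therefore enter without proteinuria.
- Primary End Points: a UPC reduction of at least 25% "from that measured before enrollment".
- Rationale of Dose: "No studies have checked the effect on proteinuria".
- Study design, Group 1: "if tolerated but response is not achieved, the dose will be escalated to Imdur 120 mg ER daily". Group 2: "The tablets of placebo will be doubled after 4 weeks of start of therapy". The active rule depends on tolerance and non-response; the placebo rule, as written, depends on neither.

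**The concern.** There are two separate points.

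**Arm size.** Independent 1:1 allocations do not fix the number in each arm. Either 20 is only an expected size and the text should say so, or a list with exactly 20 of each arm was meant and *simple* is the wrong word. Read literally, the text could also lead staff to close an arm once it holds 20 patients, after which every remaining allocation would be known.

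**Balance on UPC.** The three entry routes can mix patients with and without proteinuria, while the only primary endpoint is a fall in UPC. Baseline UPC is in hand before assignment but plays no part in it. The pilot is meant to inform a larger trial on a question that the protocol says has not been studied. A chance difference between arms in the share of proteinuric patients would make that one result harder to read.

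**Working it through.** **Inputs from the protocol:** 40 patients, 1:1 (implied), simple randomisation; UPC cut of 500 mg/g from the Inclusion Criteria. The protocol gives no power calculation, so the 20 per group can be checked only as an expectation.

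**Assumptions, not in the protocol:** the number K of the 40 patients with UPC above 500 mg/g, taken as 10 to 30; a response difference between the two UPC strata of 10 to 40 points; overall response of 20% to 50%; blocks of 4 or 6 chosen at random.

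**1. Arm size.** The number in one arm is Binomial(40, 0.5).
- Mean 40 × 0.5 = 20, which matches the stated figure; SD √(40 × 0.25) = 3.16.
- P(exactly 20:20) = C(40,20)/2^40 = 0.125.
- P(15:25 or worse) = 2 × P(X ≤ 15) = 0.154.
- Variance at 15:25 relative to 20:20: (1/15 + 1/25)/(2/20) = 1.067, so about 7% more.
- Mean efficiency: E[4·n1·n2/40²] = 1 − 1/40 = 0.975.

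**2. UPC balance.** The gap is the absolute difference between arms in the share with UPC above 500 mg/g. Under simple randomisation the proteinuric count in one arm is Bin(K, 0.5) and the non-proteinuric count is Bin(40 − K, 0.5). Both methods were enumerated exactly for K = 10 to 30.

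| | Simple | Stratified blocks of 4 and 6 |
|---|---|---|
| Mean gap | 11 to 13 points | 2 to 4 points |
| Gap of 20 points or more | 17% to 27% of trials | never (maximum 15) |
| Gap of 30 points or more | 3.5% to 8.1% | never |
| Arm sizes differ by at most 2 | – | 97% to 98% |
| Arm sizes exactly equal | 12.5% | 48% to 65% |

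An unstratified list with exactly 20 of each arm would settle the size but not the UPC balance. With K = 20, a gap of 20 points or more still occurs in about 34% of trials (simulated).

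**3. Effect on the result.** Shift in the raw response difference = gap × response difference between strata.
- At a 20-point gap: 0.20 × (0.10 to 0.40) = 2 to 8 points.
- At the mean gap: 0.112 × 0.10 = 1.1 points, up to 0.129 × 0.40 = 5.2 points.
- Standard error at 20 per arm, √(2p(1 − p)/20): 12.6 points at p = 0.2 and 15.8 points at p = 0.5.

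**4. Predictability of the blocks.** The guess is the arm that is behind in the stratum (simulated). Simple randomisation gives 50%.
- Every earlier assignment known at once: about 69% guessed correctly.
- Tablet count the only clue, both tablet rules read literally, 20% to 60% of active patients not doubled (assumed): 52% to 56%.
- The same, with the latest 4 patients' counts not yet known: 51% to 52%.

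**The case against.** The strongest reply is that this is a preference. Simple randomisation is valid, and 20 per group is ordinary shorthand for a planned size. The endpoint is already relative to each patient's own baseline, so only what prognostic effect remains matters, and its strength is unknown. A gap of 20 points or more does not occur in 73% to 83% of trials, and even then the shift is smaller than the standard error. That standard error already includes variation between strata, so the imbalance is not an extra error on top. With equal strata and 50% response overall, the stratum explains only 0.25 × 0.10²/0.25 = 1% of the response variance at a 10-point difference, and 0.25 × 0.40²/0.25 = 16% at 40 points. Adjustment in the analysis could recover much of this without any change to allocation. Blocks bring some predictability that simple randomisation does not have. Balanced arms would still contain patients without proteinuria, which is a separate matter of eligibility and endpoint.

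Most of this stands, and it is why the point ranks as minor. It does not remove the point. The stated method and the stated group size do not match without a qualifying word, and a measured baseline value tied to the endpoint goes unused. It could also be said that stratifying means waiting for a laboratory result. That adds little, because the protocol already places the UPC measurement before assignment.

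**Conclusion.** The concern holds, as an optional improvement and not as an error of validity. That 20 per group is only an expectation under simple randomisation follows from the protocol's own figures. The UPC figures rest on the assumed 10 to 30 proteinuric patients, and the 2 to 8 point shift rests also on the assumed difference in response between strata. Stratified blocks would cut the mean gap in UPC share from 11–13 points to 2–4 and remove gaps of 20 points or more. Nothing in the protocol contradicts concealment; its mechanism is simply not described.

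**What to change.** In both places that fix the method (Protocol and Treatment Plan, and Study design), replace simple randomisation with concealed 1:1 permuted-block randomisation, with block sizes varying and not disclosed to the clinic, stratified by baseline UPC above 500 mg/g (yes/no). Write *about 20 per group*, and include the stratum in the primary analysis. At the same time reconcile the Group 1 and Group 2 tablet rules, so that tablet count does not reveal the arm.

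If simple randomisation is kept on purpose, write instead: *40 patients in total, expected 20 per group; no arm will be closed early.* That sentence alone settles the arm-size point.

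The cost is one computer-generated stratified list, a sentence in two places, one term in the analysis and the reconciled tablet wording. No extra measurement is needed, but the UPC result must be available at assignment. Blocks are more predictable if past assignments become known; if nothing reveals the arm, guessing stays at 50%. A yes/no cut balances the presence of proteinuria, not its level among proteinuric patients.

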39 will be involved in safety monitoring.

40 **Possible Side Effects:**

41 Minor side effects of Imdur have been noted, including headache, dizziness, hypotension and nausea.
42 As per FDA approved package insert, headache and dizziness was reported in $>5\%$ of the patients. These
43 symptoms are dose dependent and tend to disappear with continued use.

1 Criteria for Removal:

2 With the increased dose of Imdur, if side effects such as symptomatic hypotension, nausea, headache
3 or dizziness the dose will be reduced to 60 mg ER. If it is the starting dose (60 mg ER) which caused
4 these effects, then the patient will be taken off the drug, and will be observed for Intension to Treat
5 (ITT) analysis. The Severe Adverse Effect (SAE) will be reported according to the UT Health Science
6 Center at Houston institutional policy. Criteria for removal would be uncontrolled nausea, headache,
7 symptomatic hypotension or dizziness. We will also monitor for any worsening of renal function or
8 proteinuria.

9 Limitations:

10 This is a pilot study and therefore it is may not be powered to detect difference with treatment. The small
11 sample size may not allow the data to be statistically significant. It is unclear if other antihypertensive
12 medications will confound the results. Once preliminary data is available, the study population will be
13 increased for a larger clinical trial.

14

15 Expected results:

16 There will be statistically significant response seen with therapy in the patients. The study is a pilot study
17 and will help in establishing the basis of a larger randomized controlled study.

REFERENCES:

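### Placebo tablets double at week 4 for everyone, active tablets only for tolerating non-responders, so a patient never doubled must be on active drug

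*Protocol*

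**What the plan says.** Under Study design the protocol states "The study will be double-blinded" and plans 20 patients per group. The tablet rules that follow differ by arm.

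- **Active arm (Study design, Group 1):** "after 4 weeks, if tolerated but response is not achieved, the dose will be escalated to Imdur 120 mg ER daily". The Protocol and Treatment Plan paragraph repeats the no-response condition: "escalated to 120 mg ER (two tablets of 60 mg ER) after 4 weeks of start of therapy, if no response". Dose and tablet count are therefore the same thing: one tablet is 60 mg, two are 120 mg.
- **Placebo arm (Study design, Group 2):** "The tablets of placebo will be doubled after 4 weeks of start of therapy". No response or tolerability condition is attached. The next sentence gives reduction of bias as the reason for the doubling.
- **Step-down:** Monitoring/Evaluation During Study provides for side effects at the higher dose: "dose of 120 mg/day, the dose will be reduced back to the 60 mg d". Criteria for Removal repeats this for the increased Imdur dose and takes patients with side effects at 60 mg off the drug. Neither place mentions placebo tablets.
- **Duration:** under the end points, "All patients will continue treatment for the entire 3 months to help with data analysis".

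**The concern.** A placebo schedule protects a blind only if the visible regimen has the same distribution in both arms, given what the observer knows. Here a visible feature, the number of tablets, follows a conditional rule in one arm and an unconditional rule in the other. Anyone who knows the protocol can read the arm from a patient who stays on one tablet.

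The person making the week-4 decision is worse placed still. Escalation depends on UPC, eGFR and blood pressure, so that person knows who has responded. A responder on one tablet is then active, and a responder moved to two is placebo. An arm-specific rule also requires someone to know the arm, and the protocol names no unblinded dosing role.

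The routes to bias are the judgement-based ones: as-needed ACE inhibitor or calcium channel blocker prescribing in both arms, blood pressure recorded at home and reported by the patient, and dose reduction or removal for symptoms. The Limitations section already says it is unclear whether other antihypertensives will confound the results. The primary endpoint, UPC, is a laboratory value, so it is exposed mainly through co-medication.

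**Working it through.** The protocol states no figure to reproduce. The inputs are 20 patients per group (Study design) and the tablet rules above. Week-4 response rates are not given, so they are assumptions shown as a range: r is the active-arm rate.

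**Step 1. What the rules imply.** After week 4:

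| Patient still on study drug | Active | Placebo |
|---|---|---|
| Responder | one tablet | two tablets |
| Tolerating non-responder | two tablets | two tablets |

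No placebo patient remains undoubled, so P(active | never doubled) = 1 for any r above zero.

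**Step 2. Tablet count alone.**

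- Identified as active = 20r
- P(placebo | two tablets) = 20 / (20 + 20(1 − r)) = 1 / (2 − r)
- Share guessed correctly (one tablet = active, two = placebo) = (20r + 20) / 40 = 0.5 + r/2

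| r (assumed) | Identified active | P(placebo, given two tablets) | Guessed correctly |
|---|---|---|---|
| 30% | 6 of 20 | 20/34 = 0.59 | 26/40 = 65% |
| 50% | 10 of 20 | 20/30 = 0.67 | 30/40 = 75% |
| 70% | 14 of 20 | 20/26 = 0.77 | 34/40 = 85% |

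Two tablets shift the odds towards placebo but do not prove it.

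**Step 3. Observer who also knows response.** Assume 50% response on active and 30% on placebo. The 10 active responders (one tablet) and 6 placebo responders (two tablets) are identified with certainty: 16 of 40. The remaining 10 + 14 = 24 look alike. Guessing placebo for those 24 gives (10 + 6 + 14)/40 = 75% correct. Response alone, with no tablet information, already gives (10 + 14)/40 = 60%, so for this observer the written rule adds 15 percentage points. Over assumed rates of 20–70% active and 20–40% placebo, 8 to 22 of 40 patients would be identified.

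**Step 4. Sensitivity to withdrawal at 60 mg.** If 10% of active patients come off drug, 18 remain and 18r are identified: 5.4, 9.0 or 12.6. The guess rate is unchanged if placebo loses the same share: (18r + 18)/36 = 0.5 + r/2.

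**Step 5. Under the two remedies, in the 50%/30% example.**

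- Two tablets for everyone: count carries no information, and the guess rate from count is 50%.
- Same conditional rule in both arms: P(active | one tablet) = 10/(10 + 6) = 0.625, and the guess rate is (10 + 14)/40 = 60%, which is what response alone gives.

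**Step 6. Scale for the endpoint.** One patient in 20 whose responder status changes moves that arm's rate by 1/20 = 5 percentage points. This is a unit of scale; it does not estimate the bias.

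**The case against.** The strongest reply is that the authors meant placebo to follow the Group 1 titration: the stated purpose makes sense only on that reading, and blinded clinicians could not run an arm-specific rule. That may well be the intent, but no sentence says so, and the rule as written defeats its own purpose.

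A dummy tablet could also sit in a pharmacy instruction that is not shown. The protocol assigns storage, labelling, dispensing and disposal to the research pharmacy but mentions no such tablet.

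Two points concern the meaning of one tablet. First, an active non-responder with mild symptoms might fail the tolerability condition yet stay at 60 mg. The removal rule for side effects at 60 mg points the other way, and such a patient would in any case be on active drug, so the inference about arm is unaffected. Second, if blinded staff apply the step-down to placebo as well, a current count of one no longer proves active; only a history of never having been doubled does. That qualification stands.

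Three further points stand as limits on size. For staff who know response, the fair comparison is 75% against 60%, not against 50%. UPC and eGFR are laboratory values, and clinic blood pressure is an automated average of three readings. The patients identified have already met a response criterion, when as-needed prescribing may be less active. None of these restores the blind.

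**Conclusion.** The concern holds: the dosing text is wrong as written. That a never-doubled patient must be on active drug follows from the two rules alone and needs no assumed rate. The size does: at 30–70% active response at week 4, 6 to 14 of 20 active patients are identified and tablet count gives the correct arm in 65–85% of patients. For staff who already know response, the added information is smaller, 75% against 60% in the 50%/30% example.

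The break is partial, since tolerating non-responders are alike in both arms, and its effect on UPC is indirect and cannot be quantified from the protocol. It should still be corrected: no analysis plan can restore a lost blind, and the protocol presents this pilot as the basis for a larger randomised trial. The missing placebo step-down rule is a secondary gap of the same kind.

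**What to change.** Choose one of two rules and state it for both arms.

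- **Preferred: two tablets for every patient still on study drug after week 4.** Active patients who are not escalated, or who are stepped down, take one active and one matching placebo tablet; placebo patients take two placebo tablets. Tablet count then says nothing about arm.
- **Alternative: one conditional rule.** Replace the unconditional placebo doubling with the same response, tolerability and step-down rule as in the active arm, applied by staff who do not know the allocation. Tablet count then reveals no more than response and tolerability already do.

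The active-drug dose rule is unchanged under both. The alternative needs little more than one amended sentence. The preferred rule also needs a blinded response and tolerability flag sent to the pharmacy, mixed active-plus-placebo dispensing and some extra placebo tablets. Neither needs more patients or visits.
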